## **STUDY MONITORING**

The coordinating investigator, a medical specialist and a dedicated hernia surgeon with more than 12 years of surgical experience, has the general responsibility for study monitoring and will secure that all legal and practical aspects of the study protocol are followed in all participating centers.

The coordinating investigator will receive weekly reports of performed operations from all participating centers and secure that all relevant data are submitted to a central database. If there is any baseline data missing, participants will be contacted. The database will be monitored on a weekly basis. Medical journals of all participants will be accessed on day 90 after the operation to secure all relevant data are collected. Access to data after submission will be restricted only to relevant study investigators to comply with the blinded study design. A dedicated nurse with over 15 years of experience in nursing hernia patients will contact all study participants on day 90 after operation and if there is any suspicion of deviation from the expected post operative course, participants will be called in for physical/radiological examinations. All study participants are informed to contact medical emergency services anytime if required.

# **ACCESS TO PARTICIPANTS MEDICAL RECORDS**

To ensure the safety of participants and to collect the research data upon trial completion, access to electronic patient files will be needed throughout the trial. Access to the electronic patient journal will be needed to get data on surgery performed, clinical outcomes, readmissions and CT-scans (descriptions). Patients will be asked to give explicit informed consent to data access for their electronic patient journal until the study period ends. Participants will be asked to give access to information in a 5-year period after inclusion. Information will be given about the intended use of the data as well as the intent to publish in international journals. Before participation in the study all eligible patients will be asked to give a written consent that the principal/coordinating investigator, local site investigators, sponsor, investigating nurse and eventual controlling authority may have direct access to patients medical records hereunder electronic patient journal in order to access patients medical data which is necessary for study implementation and control hereunder self-control, quality control and study monitoring. Patient data will be handled in accordance with “Databeskyttelsesloven og -forordningen”, the Danish adaptation of the European Union General Data Protection Regulation (GDPR). If patients are not interested in study participation, no data will be collected for the study.

## **Patient sensitive information**

All patient sensitive data will be anonymized prior to publication. All data protection regulations and data protection law will be followed. No data will be sent to other countries.

# **PERSPECTIVES**

One of the principles of good surgical practice is to cause as minimal surgical trauma as possible. By using mesh suture, we may substantially reduce the trauma caused by surgery. By avoiding dissection of subcutaneous tissue from underlying fascia, we preserve the perforant arteries which are usually divided and ligated. We furthermore avoid creating an artificial space between subcutis and fascia where seroma and abscesses may accrue. By reducing surgical trauma, we anticipate better QoL regarding, among others, pain, discomfort and mesh related complications such as foreign body sensations related to the surgical site. Less trauma potentially may lead to faster recovery, shorter return to work times, less use of family doctors, so we anticipate an over-all reduction in the socio-economic burden.

Our expectations are to reduce operation time by 30%, which will potentially allow us to operate on more patients per day as well as reducing waiting time to operation and thus theoretically reduce numbers of acute operations. In the planned sub-studies with longer follow-up, we will assess hernia recurrence rates to ensure that mesh suture is not inferior to planar mesh.

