## METHOD

### Study design

Multicenter, blinded, randomized controlled trial. The study is powered as a superiority study with intention to treat analysis.

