### Study population and sample size

In the literature, wound complication incidences vary greatly (from 0.7 to 63.3%), at least in part due to a lack of standardized definitions and reporting. We know that in our department the readmission rate after small ventral hernia repair is 7% (data from the National Hernia Database, 2023). The majority of these readmissions is due to wound complications. We estimate that least as many patients are treated for minor SSO in primary sector as in the hospitals (unpublished data), so the true incidence of wound complications is estimated around 14 percent for onlay mesh.

In the literature the reported *surgical site event* rate for umbilical hernias is 2.4%, with infection rates of 4.9%. For ventral hernias, surgical site events range from 1% to 8.2%, while infections range from 3.1% to 5.2%.

It is also important to note the *wound classification* in the referenced study:

- **Umbilical hernias:** 14.6% were classified as *clean-contaminated*
- **Ventral hernias:** 18.6% *clean-contaminated* and 12.4% *contaminated*

In our study, all procedures are performed in an **outpatient setting** and involve only **clean wounds**.

Additionally, **13% of patients** in the referenced cohort were **active smokers**, despite smoking being a well-established risk factor for postoperative wound complications. In our study, the rate of active smoking is **0%**, as all participants are required to be smoke-free for at least **six weeks preoperatively**, with random testing performed to verify compliance.

Based on these distinctions, our *realistic* expectation for wound complications is **1–3%**. However, to remain appropriately conservative, we have chosen to report an estimated complication rate of **4%**.

A reduction in wound complications from 14% to 4% is considered clinically significant.

A sample size of 254 participants was determined to have 80% power to detect a clinically significant between-group reduction in surgical site occurrences (seroma/hematoma formations and postoperative wound infections) from 14 to 4% and a type I error of 5%, without increase in recurrences. This number was increased to 280 participants to account for conversions and cases lost to follow-up.

No interim analyses are planned. The planned sample size is 280 patients with equal assignment to the two groups.

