## **Statistical methods**

A sample size of 254 participants was determined to have 80% power to detect a clinically significant between-group reduction in surgical site occurrences from 14 to 4% and a type I error of 5%. This number was increased to 280 participants to account for conversions and cases lost to follow-up. No interim analyses are planned.

Data will be analyzed by a blinded analyst on an intention-to-treat basis, according to the prespecified statistical plan. A two-sided P-value  $< 0.05$  is considered significant.

Analysis of the primary outcomes: Depending on the distribution of data, continuous variables will be described with mean (SD, standard deviation) or median [interquartile range (IQR)] and analyzed with students t-test or Mann-Whitney U test, respectively. Categorical variables will be described as frequencies (%) and analyzed using Fisher's exact test.

Analyses will be conducted using Stata software.

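### The protocol attaches a no-increase-in-recurrence condition to its power statement and promises non-inferiority on recurrence, but gives no margin, expected recurrence rate or power for either

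*Protocol*

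**What the plan says.** Two statements in the protocol make a claim about recurrence.

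- **Study population and sample size.** The power statement begins "A sample size of 254 participants was determined to have 80% power to detect a clinically significant between-group reduction in surgical site occurrences" and continues "from 14 to 4% and a type I error of 5%, without increase in recurrences". The total is then raised: "This number was increased to 280 participants to account for conversions and cases lost to follow-up". Allocation is equal, so 140 per arm.
- **Perspectives.** For the sub-studies with longer follow-up: "we will assess hernia recurrence rates to ensure that mesh suture is not inferior to planar mesh".

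Four other places bear on them.

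- **Study design:** "The study is powered as a superiority study with intention to treat analysis".
- **Statistical methods** repeats the sample-size statement without the recurrence condition. It sets significance at a two-sided 5% level and says: "Categorical variables will be described as frequencies (%) and analyzed using Fisher's exact test".
- **Sub-study 1** assesses recurrence at 1, 3 and 5 years. Recurrence is not listed among the primary or secondary outcomes.
- **Ethical considerations** names a possibly higher recurrence rate with mesh suture as a potential concern. It sets a stopping threshold for recurrence before 90 days in the mesh suture group, taken from a national reoperation rate of 2%.

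**The concern.** A statement of 80% power should cover only what was calculated. Read literally, the sample-size sentence says the trial has 80% power to show fewer SSOs with no increase in recurrences, which is a joint claim about two outcomes. A promise to ensure non-inferiority, in turn, has meaning only with a margin: the largest excess in recurrence that would still be accepted. Without one, no result could confirm or refute the promise.

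This matters because the Background ranks long-term recurrence with wound events as the two most important outcomes historically, and it attributes the higher recurrence after suture-only repair to the suture cutting through tissue. If mesh suture does reduce wound events, the next question will be whether that came at the price of recurrence. The protocol should say accurately what the trial can show on that question.

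**Working it through.** **1. Reproduce the plan's own figure.** Inputs from the sample-size section: p1 = 0.14, p2 = 0.04, 80% power, 5% type I error. Two-sided testing is from Statistical methods. With the mean rate p̄ = 0.09 and the pooled normal formula:

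n per arm = [1.96·√(2·p̄(1−p̄)) + 0.8416·√(p1(1−p1) + p2(1−p2))]² / (p1−p2)²

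= [1.96·√0.1638 + 0.8416·√0.1588]² / 0.01 ≈ 127.4

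This is 128 per arm (256) when rounded up, and 127 per arm (254) when rounded to the nearest integer. Power at 127 per arm is 79.9%. The stated 254 is thus reproduced from the SSO rates alone. No recurrence rate, margin or recurrence test enters.

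**2. What 140 per arm gives for recurrence.** The protocol states no expected recurrence rate at 1 to 5 years, so true rates p of 2%, 5% and 10%, equal in both arms, are **assumptions**. Also assumed: all 140 per arm are observed. With SE = √(2p(1−p)/140):

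- 95% CI half-width = 1.96·SE
- smallest margin with 80% non-inferiority power (one-sided 2.5%) = (1.96 + 0.8416)·SE
- power for a margin m = Φ(m/SE − 1.96)

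| Assumed rate | SE (points) | 95% CI half-width (points) | Smallest margin for 80% power (points) | Power, 2-point margin | Power, 3-point margin | Power, 5-point margin |
|---|---|---|---|---|---|---|
| 2% | 1.67 | 3.3 | 4.7 | 22% | 43% | 85% |
| 5% | 2.60 | 5.1 | 7.3 | 12% | 21% | 48% |
| 10% | 3.59 | 7.0 | 10.0 | 8% | 13% | 29% |

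The margins are illustrations; the protocol gives none. With 127 per arm, the number before the allowance for conversions and losses, the smallest margins rise to 4.9, 7.7 and 10.6 points.

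**3. What a difference test would detect.** Statistical methods names Fisher's exact test for categorical data. Its power at 140 per arm, two-sided 5%, to detect a doubling of recurrence was computed by summing over the two binomial distributions:

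| Recurrence, planar mesh vs mesh suture (assumed) | Fisher's exact | Normal approximation |
|---|---|---|
| 2% vs 4% | 8% | 16% |
| 5% vs 10% | 27% | 35% |
| 10% vs 20% | 59% | 65% |

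At assumed rates of 2% or 5%, a true doubling would more often than not give p > 0.05. At 10% it would be detected somewhat more often than missed.

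**The case against.** **The size of the trial may be enough.** A reader might infer that 140 per arm cannot support any non-inferiority claim. The documents do not support that. Adequacy depends on the margin: 140 per arm gives 85% power for a 5-point margin at an assumed 2% rate, and about 80% for a 10-point margin at 10%. What can be said is that no margin is stated, and that margins of 2 or 3 points are out of reach at the assumed rates (power 8% to 43%).

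**Nobody has said a non-significant result will be called safe.** A reader might also infer that a non-significant recurrence difference will be reported as non-inferior. No section says so, and Perspectives gives no decision rule. The point rests on the wording of the two claims, not on a prediction of how results will be reported.

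**A doubling would not be missed in every case.** This is right. At an assumed 10% rate, Fisher's test detects it 59% of the time, so the warning about low power holds mainly at lower rates.

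**This belongs in the statistical analysis plan.** It does in part. Recurrence is a sub-study outcome, the tests in Statistical methods are introduced as concerning the primary outcomes, and the analysis method may well stand in the separate plan. But the power statement and the promise are made in the protocol. A later plan could add a margin; it could not make the existing power statement cover recurrence.

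**The wording may be loose.** The recurrence condition may be a stray qualifier, since Statistical methods omits it, and Perspectives may use the phrase in its everyday sense. That makes correction easier, but the condition still sits inside the formal sample-size justification.

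**The 2% stopping rule protects against recurrence.** It does so only for events before 90 days, in one arm, against a reoperation rate. It supplies neither a between-arm margin nor a criterion for years 1 to 5.

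**Conclusion.** The concern holds as a point about two claims the design was never shown to support. The 80% power statement carries a recurrence condition that played no part in deriving 254, and the protocol's own repetition of that statement leaves the condition out. The non-inferiority promise has no margin, no expected rate and no power, in a study declared to be powered for superiority.

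On the assumptions in the working, the trial would estimate the recurrence difference to within about 3 to 7 points either way and could support only margins of about 5 to 10 points with 80% power. Loss to follow-up over five years would widen these figures. A non-significant difference would therefore not by itself show non-inferiority.

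The primary SSO comparison, its sample size and its test do not depend on any of this.

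**What to change.** 1. **Study population and sample size:** delete the recurrence condition from the power statement, so that it agrees with Statistical methods.
2. **Perspectives:** replace the non-inferiority promise with a statement that recurrence at 1, 3 and 5 years will be estimated as a between-arm difference with a 95% confidence interval, and that a non-significant difference will not be taken as evidence of non-inferiority.
3. **If non-inferiority is to be claimed instead of item 2:** fix a justified margin and an expected recurrence rate before any recurrence data are seen, and state the power that 140 per arm gives, allowing for expected losses. A margin chosen after the data are known would carry little weight.

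Items 1 and 2 change wording in two sections and need no extra patients or visits. The cost is a more modest stated claim about recurrence. Under item 3 the sponsor may find that the margin it can justify has low power. In that case estimation is the accurate description.

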# ETHICAL CONSIDERATIONS

Potential benefits, risks and side-effects by participation

Use of mesh suture is simple and resembles standard suture use, thus all surgeons who perform ventral hernia repair would easily be able to use the technique.

A potential concern is a potentially higher recurrence rate among patients operated with mesh suture. We will review all collected data after 3 months by a project member not otherwise involved in the project, and if early (<90 days) recurrence rates in mesh suture subgroup exceed national average reoperation rates (2%), the study will be terminated. If recurrence appears, patients will be offered standard treatment with planar mesh. It is important to mention that reoperation in case of recurrence would be easy to perform due to lack of prior extensive dissection of subcutaneous tissue and thus less fibrosis.

Patients will expectedly be subject to increased awareness regardless of whether they are randomized to the intervention group or standard treatment, as this is a known phenomenon of study participation. This may make treatment safer in both groups.

Study participants will not receive financial compensation or other benefits and will be treated according to the Helsinki declaration. Complications directly attributable to the treatment will be eligible for insurance claims from the Danish public patient insurance (“Patienterstatningen”).

## PROJECT MANAGEMENT

### Timeline and study feasibility

Due to high volume of small ventral hernia operations (2469 nationwide in 2023), the time frame estimated for patient inclusion is realistic and is estimated to be 1-2 years depending on the number of centers wishing to join the trial.

### Data analysis plan

It is estimated that completion of statistical analyses, interpretation of results and submission for publication will take 6-12 months. The analyses from sub-studies 2 will be initiated 1 year after inclusion of the last patient and are estimated to take 6-12 months to complete including submission for publication.

Table 2. Overview, project timeline

	2025				2026				2027				2028			
	Year 1				Year 2				Year 3				Year 4			
	Q1	Q2	Q3	Q4	Q1	Q2	Q3	Q4	Q1	Q2	Q3	Q4	Q1	Q2	Q3	Q4
Study preparation																
Project deescription and protocol	x	x	x													
Project registrarion at North Denmark Region			x													
Co-operation agreementa and contracts			x													
Establishment of RedCap database			x													
Study																
Recruitment and treatment of patients				x	x	x	x	x	x	x	x					
Follow-up					x	x	x	x	x	x	x	x	x	x		
Analysis																
Data management												x	x	x	x	
Analysis												x	x	x	x	
Dissemination of results																
Manuscript 1													x	x		
Manuscript 2														x	x	
Manuscript 3															x	x
Writing of PhD thesis														x	x	x

## DATA MANAGEMENT AND SECURITY

Study data are collected and managed using the encrypted REDCap electronic data capture tools hosted at Region Nordjylland. REDCap (Research Electronic Data Capture) is a secure, web-based application designed to support data capture for research studies, providing 1) an intuitive interface for validated data entry; 2) audit trails for tracking data manipulation and export procedures; 3) automated export procedures for seamless data downloads to common statistical packages; and 4) procedures for importing data from external sources.

The project will be registered in the North Denmark Region common registry for ongoing trials. When approved by the ethical board, the protocol will be made available on <https://www.clinicaltrials.gov>.

## GOOD CLINICAL PRACTICE

The project will adhere to the ICH good clinical practice (GCP) guidelines.

## PUBLICATIONS AND AUTHORSHIP

All results from the trial will be published in international peer-reviewed journals independently of study outcome. Authorship will be attributed according to the International committee of medical journal editors (ICMJE) guidelines.

## FINANCIAL ASPECTS AND CONFLICTS OF INTEREST

The study is investigator initiated and sponsored by the surgical department of Regionshospital Nordjylland, Hjørring and the Clinical Research Unit, Regionshospital Nordjylland, Hjørring and external funding will be sought. Any potential funding will be used to cover salary ([name], project nurse) and the cost of the materials. Funding will be paid to the Department of Surgery, Regionshospital Nordjylland. None of the researchers have any economic affiliations to potential funds or other entities with economic interest in the study.

## APPENDIX 1:

### Definition of SSO:

The standardized definition for surgical site infection (SSI) as defined by the Centers for Disease Control and Prevention (CDC): An infection that occurs in the part of the body where the surgery took place and includes superficial, deep, and organ space SSIs.

The standardized definition for SSO as defined by the VHWG includes any SSI as well as wound cellulitis, non-healing incisional wound, fascial disruption, skin or soft tissue ischemia, skin or soft tissue necrosis, wound serous or purulent drainage, stitch abscess, seroma, hematoma, infected or exposed mesh, or development of an enterocutaneous fistula. All complications will furthermore be classified according to the Clavien-Dindo classification system.

## APPENDIX 2:

See separate file Danish Hernia Database guidelines

## APPENDIX 3:

- **Dissect** hernia sac down to the fascia.
- **Invaginate** hernia sac and prepare fascia edges.
- **Dissect** subcutis from fascia, 2 cm from hernia edges.
- **Close** hernia defect with non-absorbable monofilament suture in transvers direction (Israelson technique).
- **Prepare** mesh. Mesh diameter = hernia diameter + min. 2 cm.
- **Fixate** mesh to fascia with non-absorbable monofilament suture.
- **Fixate** umbilicus to the fascia using absorbable suture.
- **Approximate** the subcutis to minimize dead space using absorbable suture.

## APPENDIX 4:

- **Dissect** the hernia sac down to the fascia.
- **Invaginate** the hernia sac and prepare the fascia edges.
- **Place** the first stitch 5 mm from the hernia defect.
- **Close** the fascia in a transverse direction (**Israelsson technique**).
- **Ensure** counter-tension is held on the mesh-suture to avoid entanglement while pulling through.
- **Place** the final stitch 5 mm from the hernia defect and secure it with a square knot (4 throws).
- **Fixate** the umbilicus to the fascia using an absorbable suture.
- **Approximate** the subcutis to minimize dead space using an absorbable suture.
